## 4. Data Analysis

### 4.1 Sample size

The primary outcome of this study is IAPI in patients who underwent surgery procedure.

The fixed position of surgical patients in the surgical procedure, and the occurrence of IAPI risk is time-dependent, which it is positively correlated with the advancement of time and the occurrence of IAPI events in surgical patients. For time-to-event outcomes, ensure the sample size is enough to: Estimate the overall outcome proportion with sufficient precision at one or more key time-points in follow-up; Target a shrinkage factor of 0.9; Target small optimism of 0.05 in the apparent  $R^2_{\text{Nagelkerke}}$ . The formula provided by Riley et al. is as follows:

Time-event-outcome, the sample size (number of participants, n) required to achieve the expected uniform contraction coefficient S can be expressed as:

$$n = \frac{P}{(S-1)\ln\left(1 - \frac{R_{cs}^2}{S}\right)}$$

To calculate the sample size, to ensure that the expected optimistic value of  $R^2$  (i.e.,  $R_{cs}^2/\max(R_{cs}^2)$ ) has a smaller expected optimism. For time-event-outcome, the first step is to calculate the contraction coefficient corresponding to the expected optimistic value in  $R^2_{\text{Nagelkerke}}$ :

$$S = \frac{R_{cs}^2}{R_{cs}^2 + \delta\max(R_{cs}^2)}$$

The recent randomized controlled trial results showed an incidence of IAPI (stage I and above) of 13.9%, assuming 0.05 acceptable difference in apparent & adjusted

R-squared. The study used the R4.1.2 software (pmsampsize package) to estimate the minimum sample size required to develop the new model. Minimum sample size required for new model development is 4115, with 572 events (assuming an outcome prevalence = 0.139) and an Events per Predictor Parameter (EPP) is 23.83. In addition, according to the pre-model design requirements, the total sample was divided into 80% samples for the development of the new model and 20% samples for the validation of the model. This means that a total of 5144 cases are required. Considering a possible 10% loss of follow-up, the minimum sample size required for the prediction model was 5658 cases.

```
NB: Assuming 0.05 acceptable difference in apparent & adjusted R-squared
NB: Assuming 0.05 margin of error in estimation of intercept
NB: Events per Predictor Parameter (EPP) assumes prevalence = 0.139
```

	Samp_size	Shrinkage	Parameter	CS_Rsq	Max_Rsq	Nag_Rsq

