Criteria 1	4115	0.900	24	0.051	0.553	0.092
Criteria 2	833	0.648	24	0.051	0.553	0.092
Criteria 3	184	0.900	24	0.051	0.553	0.092
Final	4115	0.900	24	0.051	0.553	0.092
		EPP				
Criteria 1	23.83					
Criteria 2	4.82					
Criteria 3	1.07					
Final	23.83					

```
Minimum sample size required for new model development based on user inputs = 4115,
with 572 events (assuming an outcome prevalence = 0.139) and an EPP = 23.83
```

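### The 10% loss-to-follow-up allowance is added rather than divided out, so enrolling 5658 leaves about 5092 patients, short of the 5144 the plan requires

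*Combined protocol and SAP*

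**What the plan says.** Section 4.1 (Sample size) reaches the enrolment figure in three steps.

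1. Development set, from the pmsampsize output: "Minimum sample size required for new model development based on user inputs = 4115". The expected number of events is 572, at an assumed prevalence of 0.139.
2. Data split: "the total sample was divided into 80% samples for the development of the new model and 20% samples for the validation of the model". The resulting total is given as: "This means that a total of 5144 cases are required".
3. Attrition: "Considering a possible 10% loss of follow-up, the minimum sample size required for the prediction model was 5658 cases".

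No formula is given for step 3. The section does not say whether the 10% is a share of those enrolled or of those required, nor by what time point a patient counts as lost. Section 5.1 allows withdrawal at any time, and no section provides for replacing patients who are lost.

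**The concern.** A loss rate acts on the patients who enter the study. If 10% of N enrolled patients are lost, 0.90 × N remain, so N must be the required number divided by 0.90. Adding 10% to the required number always gives too few, because 1.10 × 0.90 = 0.99: about 1% of the requirement is missing whatever the starting figure.

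The plan uses the right logic one step earlier. For the 80/20 split it divides 4115 by the fraction retained for development (0.8); it does not add 20%. Attrition is the same kind of problem but is handled differently.

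At stake is whether the only enrolment target in the documents delivers the development set, events and shrinkage claimed for it. The development criterion offers no slack, because 4115 comes from the binding criterion; the other two need only 833 and 184.

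**Working it through.** **Inputs, all from Section 4.1 and its pmsampsize output**

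- Predictor parameters P = 24, target shrinkage S = 0.900, Cox-Snell R² = 0.051 (output row "4115 0.900 24 0.051 0.553 0.092")
- Assumed prevalence 0.139
- Development share 80%
- Loss to follow-up 10%

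**Reproducing the plan's figures**

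- Criterion 1: n = P / [(S − 1) ln(1 − R²/S)] = 24 / [(−0.1) × ln(1 − 0.051/0.9)] = 4114.1, rounded up to 4115. This agrees.
- Events: 4115 × 0.139 = 572.0. Per parameter: 572.0 / 24 = 23.83. Both agree.
- Split: 4115 / 0.80 = 5143.75, rounded up to 5144. This agrees.
- Attrition as the plan appears to have done it: 5144 × 1.10 = 5658.4, stated as 5658. (Rounding down instead of up to 5659 is trivial.)
- Attrition by dividing: 5144 / 0.90 = 5715.6, rounded up to 5716. This does not give 5658.

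**What 5658 delivers at 10% loss**

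| Quantity | Calculation | Result | Plan's figure | Shortfall |
|---|---|---|---|---|
| Patients remaining | 5658 × 0.90 | 5092.2 | 5144 | 52 (1.0%) |
| Development set | 5092.2 × 0.80 | 4073.8 | 4115 | 41 |
| Expected events | 4073.8 × 0.139 | 566.3 | 572 | 6 |
| Events per parameter | 566.3 / 24 | 23.59 | 23.83 | 0.24 |

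Expected shrinkage: solving 24 / [(S − 1) ln(1 − 0.051/S)] = 4073.8 for S gives about 0.899, against 0.900.

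**Loss that 5658 covers:** (5658 − 5144) / 5658 = 514 / 5658 = 9.1%.

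**Check of the corrected figure:** 5716 × 0.90 = 5144.4, and 5144.4 × 0.80 = 4115.5. Both requirements are met. The difference in enrolment is 5716 − 5658 = 58, or 1.0% of 5658.

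**The case against.** The arithmetic cannot reasonably be disputed; the case on the other side is about consequence and interpretation.

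- **The effect is negligible.** A shrinkage of 0.899 is 0.9 at the precision of the stated target. By the plan's formula, a Cox-Snell R² of 0.0515 instead of 0.051 lowers the required development set from about 4114 to about 4073, so a change of 0.0005 in an assumed input is worth the whole shortfall. The event count rests on an assumed 13.9%, while the Introduction cites incidences from 4.9% to 66.0%. All of this stands, and it limits how much weight the point deserves.
- **Not every lost patient lacks the outcome.** The Abstract sets the primary outcome at 7 days, while follow-up runs to three months. A patient lost after day 7 could still enter the model. This stands as a qualification: the figures 5092, 4074 and 566 assume that all the loss occurs before the pressure-injury outcome is known. It does not justify 5658, because Section 4.1 itself applies the 10% to the number needed for the model.
- **5658 is a minimum, not a cap.** Eligibility in Section 2.4 is broad and nothing stops recruitment at 5658, so the study may exceed it. That is true, but a stated minimum should be sufficient if it is only just reached.
- **The 10% might be a share of the 5144 required.** On that reading 5658 is right to rounding. The documents do not define the loss that way, and a share of those enrolled is the usual meaning.

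**Conclusion.** The concern holds. The figure 5658 comes from adding 10% to 5144, and at the plan's own attrition rate it misses both the total of 5144 (by about 52) and the development minimum of 4115 (by about 41). The enrolment figure consistent with Section 4.1's other numbers is 5716.

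The error is minor, about 1% of enrolment, and no analysis or conclusion is shown to change because of it. It deserves correction because the plan relies on the figure as its minimum and the arithmetic is easily checked. The conclusion assumes that the 10% is a share of enrolled patients, that lost patients have no usable primary outcome, and that they are not replaced. It takes the 24 parameters, the R² and the 13.9% as given and does not judge whether they are suitable.

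**What to change.** Amend the attrition sentence in Section 4.1 in one of two ways:

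- restate the minimum as 5716, showing 5144 / 0.90. This adds 58 patients, about 1%, to the target; or
- keep 5658, state that it covers a loss of 9.1% of those enrolled, and report that at 10% loss the development set would be about 4074 with about 566 expected events. This needs no extra patients.

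In either case, say that the percentage refers to enrolled patients without a usable primary outcome, and state the time point by which that is judged. The cost is an edit to one short passage.

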#### **4.2 Data analysis**

This study is divided into two distinct sections. The aim of the first part is to create and validate a IAPI risk score for individuals from the whole cohort, predicting their individual IAPI values using a combination of potential predictive variables. The aim of the second part is to evaluate whether the IAPI score is helpful in predicting 90-day mortality in individuals from the whole cohort. We also evaluated the incidence and attributable mortality to IAPI, SSI, and surgical complications in patients admitted for

surgical procedures during the same study period.

All statistical analyses were performed with R (the latest version; R Foundation for Statistical Computing) and Python (the latest version; Python Software Foundation). All tests conducted in this study were 2-tailed, and  $P < 0.05$  was deemed statistically significant.

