#### ***4.2.1 Model development***

The entire cohort is randomly divided into two datasets: a training cohort (80%), which will potentially be utilized for training twelve machine learning models and optimizing their parameters, and an internal validation cohort (20%), which was employed to evaluate the developed models on unseen data and refine the hyperparameters.

The variable selection process in the development sample will be conducted using a recursive feature elimination (RFE) algorithm. RFE ranks the most relevant predictors in a dataset by training models with and without all potential predictor combinations. To identify the optimal number of variables, we will assess the incremental gain in predictive performance associated with each variable and stop at the inflection point. RFE is an iterative process that starts with all possible features in the dataset and progressively removes the least relevant features, building a model after each iteration. The goal is to find the optimal subset of features that maximizes the predictive power of the model. In each iteration, RFE evaluates the performance of the model with and without a specific feature and removes the feature if its removal results in a significant improvement in model performance. This process is repeated until the

desired number of features is reached or a stopping criterion is met. The inflexion point is the point at which the incremental gain in predictive performance begins to decrease significantly. Identifying the inflexion point helps to ensure that the final model does not overfit the data and can generalize well to new data. In conclusion, by using the RFE algorithm and identifying the inflexion point, the development sample will undergo a thorough variable selection process, ensuring that the final model is as predictive as possible while avoiding overfitting.

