After variable selection with RFE, we will be trained potential seven statistical models with centred and scaled selected predictors because of the different scales of the predictors and to ease the intercept of models to the IAPI, including a logistic regression, decision tree, random forest, artificial neural network (ANN), eXtreme Gradient Boosting algorithm (XGBoost), support vector machine (SVM), k-nearest neighbors (k-NN). Logistic regression is suitable for binary classification problems, while decision trees can handle both binary and multi-class problems. Random forests and XGBoost are based on decision trees and are known for their good performance in predicting both continuous and categorical variables. ANNs can be used for nonlinear problems, but they require more time for training. SVM and k-NN are also popular for classification problems, but they require different preprocessing techniques.

To evaluate the performance of each model, we will be using the cross-validation. With k-fold cross-validation, the data is randomly divided into k subsets, and each model is trained on k-1 subsets and tested on one subset. This process is repeated k times, with each of the k subsets being used once as the test set. The average

performance across all k tests is then used as the final performance measure. To assess the degree of potential over-fitting of each algorithm, we will be trained them using a 10-fold 10-repeat cross-validation procedure.

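### The plan tests the IAPI score against 90-day mortality in a cohort that is 80% training patients and does not require out-of-fold or held-out scores; a flexible model could then look too prognostic

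*Combined protocol and SAP*

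**What the plan says.** Section 4.2 divides the analysis into two parts. The first is to "create and validate a IAPI risk score for individuals from the whole cohort"; the second is to "evaluate whether the IAPI score is helpful in predicting 90-day mortality in individuals from the whole cohort".

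Section 4.2.1 describes the split: "a training cohort (80%), which will potentially be utilized for training twelve machine learning models". The remaining 20% is a validation set, "which was employed to evaluate the developed models on unseen data and refine the hyperparameters". The candidates are given as "including a logistic regression, decision tree, random forest", followed by a neural network, XGBoost, SVM and k-NN. Variables are selected by RFE first. Cross-validation comes afterwards, to measure each algorithm's performance and over-fitting: "trained them using a 10-fold 10-repeat cross-validation procedure".

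Section 4.2.3 relates observed IAPI to mortality and gives no method for relating the score to mortality. Section 4.2.4.2 speaks in favour of a logistic points score as an alternative, while the Abstract leaves the final algorithm to whichever performs best. The Abstract also treats data not used in training as the proper basis for judging prediction of IAPI. Nowhere is that principle extended to mortality.

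**The concern.** The score is trained on IAPI and not on death, so testing it against death in the training patients may look harmless. That is not so for flexible algorithms. In a training patient, the fitted value of a deep tree, forest or boosted model can reproduce part of that patient's own IAPI outcome, which is known only after surgery. The plan expects pressure injury to be associated with death (Introduction and section 2.5.2). If part of that association remains once the predictors are known, the in-sample score brings the later IAPI event into the mortality prediction. A score computed for a new patient cannot do this.

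At stake is the second aim. The score's discrimination for death, and the mortality contrast between its risk groups, would mix the score's own prognostic value with that of IAPI.

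**Working it through.** **1. The plan's own figures.** Section 4.1 gives P = 24, S = 0.9 and Cox-Snell R² = 0.051.

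n = P / [(S − 1) ln(1 − R²/S)] = 24 / [(−0.1) × ln(1 − 0.051/0.9)] = 24 / 0.005834, which rounds up to 4115.

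Events: 0.139 × 4115 = 572, and 572/24 = 23.83 per parameter. Total: 4115/0.8 = 5144; with the 10% allowance, 5144 × 1.1 = 5658. These all reproduce. The plan states no figure for the score-mortality analysis.

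**2. Main simulation.**
- From the documents: 5144 patients, 4115 in training, IAPI 13.9%, R² 0.051.
- Assumed: 24 independent normal predictors (10 informative); 2% mortality (section 4.2.3 says only that death is expected to be rare); predictors' own effect on death half their effect on IAPI; IAPI-death odds ratio given the predictors (residual OR) of 1, 1.5, 2 or 3.
- Five training sets, each compared with 20,000 new patients. Out-of-fold scores here came from 5 folds.

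Optimism is the AUC for death in the whole cohort, using training-set predictions, minus the AUC in new patients. Differences were taken before rounding; their Monte Carlo standard errors are at most 0.002.

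| Model | AUC for IAPI, training / new | OR 1 | OR 1.5 | OR 2 | OR 3 |
|---|---|---|---|---|---|
| Forest, fully grown | 1.00 / 0.61 | −0.013 | +0.008 | +0.026 | +0.054 |
| Forest, leaf size 20 | 0.97 / 0.65 | −0.004 | +0.010 | +0.022 | +0.042 |
| XGBoost, default | 1.00 / 0.60 | −0.005 | +0.014 | +0.031 | +0.058 |
| Boosting, shallow | 0.80 / 0.64 | +0.001 | +0.008 | +0.014 | +0.023 |
| Logistic | 0.69 / 0.67 | 0.000 | +0.001 | +0.001 | +0.002 |

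The optimism grows with the residual OR and with how closely the model fits its own training patients.

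**3. Does out-of-fold scoring remove it?** AUC for death at OR 3, whole cohort in-sample, then out-of-fold, then new patients:
- fully grown forest: 0.634, 0.579, 0.579
- forest with leaf size 20: 0.646, 0.603, 0.604
- default XGBoost: 0.635, 0.575, 0.577
- shallow boosting: 0.627, 0.601, 0.603
- logistic: 0.627, 0.623, 0.624

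Out-of-fold values lie within 0.002 of the new-patient values.

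**4. Categorical predictors and tuning.** Table 1 items are mostly categorical, and the plan intends to select variables and tune.
- Twelve three-level predictors, OR 3, whole cohort against new patients: fully grown forest 0.637 vs 0.582 (out-of-fold 0.579); default XGBoost 0.626 vs 0.564 (0.561); heavily regularised forest 0.622 vs 0.616; shallow boosting 0.619 vs 0.615; logistic 0.621 vs 0.621.
- Dichotomous or four-level predictors (8 or 24), four replicates, tuned by 3-fold cross-validation. Optimism for tuned XGBoost was 0.001 to 0.006 at OR 2 and 0.002 to 0.011 at OR 3. For a tuned forest it was 0.004 to 0.012 and 0.006 to 0.022. Without tuning, the forest and default XGBoost gave 0.015 to 0.038 and 0.029 to 0.067.

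**5. Deaths available.** The 20% set has 5144 − 4115 = 1029 patients. At an assumed 1% to 3% mortality that is about 10 to 31 deaths, against about 51 to 154 in all 5144. Restricting the mortality test to the 20% set would remove the bias but lose most of the deaths.

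**The case against.** **The phrase may name a population and not a scoring method.** Section 4.2 uses the same words for part one, which is then split 80/20 and assessed in the validation set. A reader might infer that the plan has prescribed in-sample scores for mortality. It has not: it names the whole cohort and is silent on which scores are used. But because section 4.2.3 gives no method for this aim, an analyst who applies the final model to everyone would be following the plan.

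**The models will be tuned.** The Abstract plans cross-validation or grid search, and section 4.2.1 plans RFE. This stands and cuts the size considerably. A reader might infer that a flexible score in a training patient nearly equals that patient's IAPI status. This is true of fully grown forests and default XGBoost, but the tuned models had a training AUC for IAPI of only 0.68 to 0.82. Single decision trees were not simulated.

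**Logistic regression may be chosen.** Section 4.2.4.2 favours it, and it suits the aim of a simple score. In that case the bias is negligible. The plan does not fix the choice, however.

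**The residual link may be weak.** The Introduction itself suggests that pressure injury reflects poor health more than it causes death. At a residual OR of 1.5 the tree-based models show only 0.008 to 0.014, and at 1 no upward bias. It therefore cannot be said without conditions that the mortality results would fail to reproduce in new patients.

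**Conclusion.** The point holds conditionally. Followed as written, the plan allows a mortality evaluation in which 80% of the scores come from a model fitted to those patients' own IAPI outcomes. The result is too favourable if the final model is flexible and IAPI predicts death beyond the predictors.

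Under assumptions that the documents do not supply (2% mortality, residual OR 1.5 to 3), the AUC optimism is about 0.01 to 0.07 for untuned or fully grown forest and boosted models and about 0.00 to 0.02 for well-tuned ones. It is nil for logistic regression and does not arise at a residual OR of 1.

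Two wider inferences are not supported. The assessment of IAPI prediction in section 4.2.2 is made in the validation set and is not affected by this mechanism. The attributable-mortality analysis in section 4.2.3 uses observed IAPI and not the score. The point concerns the second aim only, but a safeguard should be specified while the algorithm is still open.

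**What to change.** In sections 4.2 and 4.2.3, add the method for the score-mortality aim and state that:
- each training patient's score is the out-of-fold prediction from the planned 10-fold, 10-repeat cross-validation, averaged over the ten repeats;
- RFE and tuning are carried out inside the folds, so that no training patient's score depends on that patient's own IAPI outcome;
- patients in the 20% set receive the prediction of the locked model, and that set is not used to refine hyperparameters. Section 4.2.1 must be changed on this point, which also brings it into line with the Abstract, where the set stays untouched during development.

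The rule can be written now for any algorithm and keeps all deaths in the analysis.

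The cost is SAP wording and some computing. Saving predictions from the cross-validation as now planned is not enough, because section 4.2.1 runs it after RFE. RFE and tuning must be rerun in up to 10 × 10 = 100 training folds, but only for the final algorithm. No new data are needed. The reported AUC for mortality may be slightly lower.

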### **Methods:**

We will use a pre-set observational assessment scale that consists of 24 indicators to construct the predictive model in this study. In addition to these pre-set indicators, the researchers will also collect other relevant indicators that they believe may contribute to the predictive model. Primary outcome was incidence of IAPI of any stage at 7 days from operating room admission. Secondary outcomes were in-hospital mortality (follow-up endpoint is 3 months after surgical procedure), surgical complication, and hospitalization costs. The prospective cohort study dataset is divided randomly into two

subsets: a training group (80% of the data) and an internal validation group (20% of the data). The training group is used for model development, while the internal validation group remains untouched until later stages. In model development, researchers can explore different variables and test various machine learning algorithms, such as logistic regression, artificial neural network (ANN), XGBoost, support vector machine (SVM), k-nearest neighbors (k-NN), naive Bayes, gradient boosting machines (GBM), AdaBoost, Gaussian mixture model (GMM), and support vector regression (SVR). They can train and optimize these models using the training dataset. After training the models on the training dataset, researchers can evaluate their performance using appropriate evaluation metrics (e.g., accuracy, precision, recall, F1-score, area under the receiver operating characteristics curve). Based on the evaluation results, we refine the model by tweaking hyperparameters, feature selection, or employing techniques like cross-validation or grid search. This iterative process aims to find the best-performing model configuration. Once the model is optimized using the training dataset, it is then evaluated on the internal validation dataset. This evaluation serves as an unbiased assessment of the model's performance on unseen data, providing an estimate of its ability to generalize. Based on the performance on the internal validation dataset, to choose the best-performing model as the final predictive model.

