### ***2.5.2 Secondary outcome***

The secondary outcome of this study is in-hospital mortality, which refers to the number of patients who die from any cause while receiving surgical procedure in a hospital. The data from a large sample of 13,254 patients in 1117 ICUs across 90 countries revealed that patients with pressure injuries (PI) exhibited a significantly higher mortality rate compared to those without PI. Furthermore, there was a gradual increase in the correlation between the severity of pressure injury and mortality rate.

Surgical site infections (SSIs) will also be observed, SSIs are infections of the incision or organ or space that occur after surgery. Sepsis is defined as life-threatening organ dysfunction caused by a dysregulated host response to infection, the subsequent statement presents the diagnostic criteria in accordance with the Third International Consensus Definition of sepsis:

- Organ dysfunction can be identified as an acute change in total Sequential Organ Failure Assessment (SOFA) score  $\geq 2$  points consequent to the infection.
  - The baseline SOFA score can be assumed to be zero in patients not known to have preexisting organ dysfunction.
  - An ASOFA score  $\geq 2$  reflects an overall mortality risk of approximately 10% in a general hospital population with suspected infection. Even patients presenting with modest dysfunction can deteriorate further, emphasizing the seriousness of this condition and the need for prompt and appropriate intervention, if not already being instituted.
- In lay terms, sepsis is a life-threatening condition that arises when the body's

response to an infection injures its own tissues and organs.

- Patients with suspected infection who are likely to have a prolonged ICU stay or to die in the hospital can be promptly identified at the bedside with quick SOFA, ie, alteration in mental status, systolic blood pressure  $\leq 100$  mmHg, or respiratory rate  $\geq 22$ /min.
- Septic shock is a subset of sepsis in which underlying circulatory and cellular/metabolic abnormalities are profound enough to substantially increase mortality.

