### ***2.6 Follow-up period***

The clinical follow-up will be conducted at 0.5, 2-, 24-, 48-, 72-hours and 7 days post-surgery, as well as at the three-month mark following the completion of the surgical procedure during in-hospital. The investigator has the flexibility to carry out these follow-ups either through telephone communication or in-person office visits.

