#### 3.2 Data collection tools and instruments

The data collection will be facilitated through a network-based data infrastructure, where in the potential predictor variables are comprehensively described in [Table 1](#). Further details can be accessed on the website <https://www.wjx.cn/>. Prior to sample inclusion, data collectors at all participation centers underwent mandatory homogenization training. The clinical follow-up will be conducted at 0.5, 2, 24, 48, and 72 hours post-surgical procedure, as well as at the three-month mark following the completion of the surgical procedure. The investigator has the flexibility to carry out these follow-ups either through ward visit, telephone communication or follow-up appointments for outpatient care.

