#### ***4.2.3 Secondary outcome assessment***

The secondary outcome of this study is in-hospital mortality, survival analysis, including Kaplan-Meier analysis and log-rank testing, was used to evaluate the association between IAPI and various patient characteristics. Generalized linear mixed-effects regression analysis with a logit link function and a random effect for country was used to account for possible confounding factors. Odds ratios and 95% confidence intervals were used to present the results. We assumed that the occurrence of in-hospital mortality would be rare, ensuring that odds ratio estimates derived from a case-control design could serve as reliable estimators of relative risk for calculating the IAPI mortality attributable fraction. The following approach was used for attributable fraction calculation for each admission type: the inverted probability weights (IPW) for each patient were calculated, representing the cumulative risk of the patient acquiring IAPI during hospitalization, under a multivariable logistic regression analysis including baseline age, Charlson Comorbidity Index, surgical complications, and a time-dependent variable for the occurrence of clinically relevant events. We estimated the association between IAPI occurrence on hospital mortality post operation three months through a mixed logistic regression model weighted by IPW. The delta method was employed to compute the 95% CIs for both the odds ratio and attributable mortality.

We also assessed the incidence and attributable mortality of surgical complications in patients during the same hospitalization by . Additionally, we evaluated the duration of hospital stay and associated costs incurred by patients within this hospitalization period.

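### The mortality endpoint is not fixed: the plan moves between in-hospital death and death to day 90, with no rule for deaths after discharge

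*Combined protocol and SAP*

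**What the plan says.** The combined protocol and SAP describes mortality in these ways:

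- **Abstract, Methods:** "Secondary outcomes were in-hospital mortality (follow-up endpoint is 3 months after surgical procedure".
- **Section 2.5.2:** in-hospital mortality "refers to the number of patients who die from any cause while receiving surgical procedure in a hospital".
- **Section 4.2:** the second part of the study is to "evaluate whether the IAPI score is helpful in predicting 90-day mortality in individuals from the whole cohort".
- **Section 4.2.3, opening:** "The secondary outcome of this study is in-hospital mortality".
- **Section 4.2.3, weighted model:** "We estimated the association between IAPI occurrence on hospital mortality post operation three months".

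The follow-up text is also divided. Section 2.6 places the last contact "as well as at the three-month mark following the completion of the surgical procedure during in-hospital". Section 3.2 has the same three-month contact made "either through ward visit, telephone communication or follow-up appointments for outpatient care", which reaches patients who have gone home. Section 3.3 asks for source documents for deaths within 3 months, and Table 2 schedules death at every contact from 0.5 hours to 3 months.

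Section 4.2.3 uses the mortality odds ratio as a stand-in for relative risk, on the assumption that in-hospital death is rare, and derives an attributable fraction for IAPI from it. The weighting model names age, the Charlson index, surgical complications and a time-dependent variable whose content is not specified. Length of stay appears only as an outcome to be described.

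**The concern.** Two analysts following this text could count different deaths. One would stop at discharge; the other would count every death to day 90. Neither would be contradicting the plan, because no section gives a rule for a death after discharge but before day 90. The 90-day endpoint in Section 4.2 is never listed as an outcome, and Section 4.2.3 describes no analysis relating the risk score to death.

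The choice can change the answer. In-hospital death is observed only for as long as the patient stays, so a group that stays longer has more time in which a death can be counted. If IAPI goes with longer stay, part of any association between IAPI and in-hospital death can reflect observation time. That association feeds the attributable-mortality estimate.

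**Working it through.** **The plan's own figures.** No mortality rate, death count or power for mortality is given, so there is nothing to reproduce on this point. The sample-size figure does reproduce: 24 / [(0.9 − 1) × ln(1 − 0.051/0.9)] = 4114.1, so 4115. It concerns the IAPI model only.

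**Which labels conflict.** Ninety days and three months are effectively the same window. The wording in Section 2.5.2 sits inside a definition of in-hospital mortality, and Table 2 follows death to 3 months, so it is probably loose wording for the surgical admission. That leaves in-hospital death against all deaths to day 90.

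**Length-of-stay effect, closed form.** Assume a constant daily death hazard h, the same with and without IAPI, and exponential time to discharge with mean L.

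- P(in-hospital death) = h / (h + 1/L), so the odds are hL.
- The null odds ratio is hL1 / hL0 = L1/L0, whatever h is.
- With L0 = 10 days and L1 = 12, 15 or 20 days, the odds ratio is 1.2, 1.5 or 2.0.

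The stays are assumed; the documents give none by IAPI status.

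**Carry-through to the attributable fraction.** The plan does not state its formula. Taking Levin's formula, p(OR − 1) / [1 + p(OR − 1)], with the plan's IAPI incidence p = 0.139:

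- OR 1.2: 0.0278 / 1.0278 = 2.7%
- OR 1.5: 0.0695 / 1.0695 = 6.5%
- OR 2.0: 0.139 / 1.139 = 12.2%

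These would be shares of deaths attributed to IAPI when it has no effect.

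**Simulation with a different stay distribution.** There were 4 million patients per scenario and no effect of IAPI on death. Assumptions from outside the documents are 90-day mortality of 3% (constant hazard except in the last two rows) and lognormal stay with median 7 days and log-SD 0.7. IAPI incidence is 13.9%, from the plan.

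| Scenario | OR, in-hospital death | OR, 90-day death |
|---|---|---|
| IAPI unrelated to stay | 1.03 | 1.00 |
| Stay 1.25 times longer with IAPI | 1.27 | 1.00 |
| Stay 1.5 times longer | 1.49 | 1.00 |
| Stay 2 times longer | 2.10 | 1.01 |
| IAPI odds rise with stay (log-OR 0.5 per SD) | 1.42 | 0.99 |
| IAPI counted only if it precedes death, stay unrelated | 0.77 | 0.98 |
| Same, stay 1.5 times longer | 1.25 | 0.97 |
| Same, 40% of deaths in first 7 days, stay unrelated | 0.70 | 0.88 |
| Same, 40% early deaths, stay 1.5 times longer | 0.85 | 0.87 |

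The 1.03 in the first row is noise. In-hospital deaths number about 4,000,000 × 0.0030 = 12,000, of which about 1,668 have IAPI. The standard error of the log odds ratio is then √(1/1668 + 1/10332) = 0.026, and ln 1.03 = 0.030.

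**How many deaths the label moves.** In the first scenario, in-hospital mortality was 0.30% against 3.00% at day 90. In the plan's 5144 patients that is about 15 deaths against 154. The gap narrows if deaths cluster early.

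**The case against.** A reader might infer that an in-hospital endpoint necessarily creates a false link between IAPI and death. The documents do not support that. They give no stay by IAPI status and do not say that IAPI prolongs stay. Without that association the simulation shows no spurious effect, and when early death prevents IAPI from being recorded the net bias can run the other way (0.70 to 0.85 with 40% of deaths in the first week). The figures 1.2 to 2.0 restate the assumed stay ratios, and they are crude, whereas the planned model is weighted. The unspecified time-dependent variable might absorb part of the problem. All of this stands, and it limits the bias to a qualified risk.

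A reader might also take Section 2.5.2 literally, as death during the operation. Its context and Table 2 make that unlikely.

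It can further be said that two endpoints are intended: in-hospital death for the IAPI association and 90-day death for the score. That is possible, but the plan never says so. In-hospital death with discharge handled as a competing event would also be defensible, but Section 4.2.3 does not describe that, and its weighting model names neither stay nor discharge. Finally, mortality is secondary, and the IAPI prediction model is unaffected. That limits how far the defect reaches but does not remove it, because predicting death is a stated aim of the second part.

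**Conclusion.** The endpoint conflict is established from the text: in-hospital death and death to day 90 are both in use, and deaths after discharge have no rule. It should be settled before analysis, since a stated aim and the attributable-mortality estimate depend on it.

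The bias through length of stay is a risk and has not been demonstrated. Given a constant hazard, no true effect and an association between IAPI and longer stay, the crude in-hospital odds ratio is roughly the ratio of mean stays, for example 1.2 to 2.0 for stays 1.2 to 2 times longer. Its net direction is not established. A fixed 90-day endpoint removes the length-of-stay part (0.99 to 1.01 in the scenarios without early-death bias). It does not remove the early-death part (0.87 to 0.98), so it should not be read as a complete cure.

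**What to change.** 1. In the Abstract and Sections 2.5.2, 4.2 and 4.2.3, define one mortality endpoint: all-cause death within 90 days of surgery, counted whether or not the patient has been discharged. Use it for both the score-prediction aim and the IAPI attributable-mortality analysis.
2. Report in-hospital death as a labelled descriptive outcome, and delete from Section 2.5.2 the phrase that ties death to the procedure itself.
3. In Section 4.2.3, add the missing analysis of the score against 90-day death.
4. Reconcile the in-hospital qualifier in Section 2.6 with Sections 3.2 and 3.3 and Table 2.
5. State how deaths before IAPI could be recorded are handled, for example with IAPI as a time-dependent exposure or a landmark analysis at day 7.

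**Cost.** These are text changes and a little extra analysis. Death is already scheduled to 3 months, with telephone contact allowed and source documents required, so no new visit is needed. The price is that deaths after discharge depend on reaching patients or families. Section 4.1 allows for 10% loss to follow-up, so the report should give the number with unknown vital status at day 90 and a sensitivity analysis for them.
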